8.10.7.4. Time to Derived Organ Progression

The following time-to progression endpoints will be analyzed in the same manner described in Section 8.10.7.1. For all of the endpoints below, subjects who die prior to having documented disease progression will be assumed to have progressed at their date of death and subjects who discontinue due to disease progression, as reported on the ETD or EOS eCRF, will be assumed to have progressed at the date of their last contact.

- Time (months) to cardiac progression calculated as: (date first assessed with progression (Section 8.7) - the date of first study drug infusion + 1) / 30.4375. Subjects who do not experience progression will be censored at the date of last NT-proBNP assessment.
- For renal evaluable subjects, time (months) to renal progression calculated as: (date first assessed with progression (Section 8.9.1) - the date of first study drug infusion + 1) /

30.4375. Subjects who do not progress will be censored at the date of last eGFR assessment.

- Time (months) to cardiac or renal progression calculated as: (earliest date assessed as a NT-proBNP or renal progressor - the date of first study drug infusion + 1) / 30.4375. Subjects who do not progress will be censored at the minimum of the last NT-proBNP assessment date or last eGFR assessment date.

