4.3 Early Treatment Discontinuation

If the subject discontinues study drug prior to the EOS Visit, they should return for an ETD Visit 30 (\pm 5) days after their final administration of study drug as per [Section 6.2](#). If a subject fails to return for the scheduled visit, a documented effort must be made to determine the reason. If the subject cannot be reached by telephone after 2 attempts, a certified letter will be sent to the subject (or the subject's legally authorized representative, if appropriate) requesting contact with the Investigator. This information will be recorded in the study records.

If the subject discontinues study drug prior to the EOS, but is willing to continue to participate in study visits, the subject should have an ETD Visit 30 (\pm 5) days after his/her final administration of study drug (per [Section 6.2](#)) and then have assessments monthly, through Month 12 per [Appendix 13](#). The subject will not have an EOS Visit. The most important visit is the Month 12-Day 1 Visit, so if a subject is unwilling to continue monthly visits, every effort should be made for the subject to return to the clinic and complete the Month 12-Day 1 Visit on schedule. All visits after the ETD Visit should occur on schedule, that is, at the time when their visit would have occurred had they remained on study drug. Following the Month 12-Day 1 Visit, subjects will be followed for vital status per [Section 6.4](#).

Reasons for early discontinuation from study drug treatment may include, but are not limited to:

- Hematologic progression and initiation of chemotherapy is required; chemotherapy regimen should be documented on the appropriate electronic case report form (eCRF).
- Need for organ transplant or major surgery.
- A suspected NEOD001-related immunologic reaction – collect additional serum samples, if possible, during the period following the treatment stoppage to allow for the determination of the persistence of anti-NEOD001 antibodies. At a minimum, samples should be collected at the ETD Visit and 3 months after the ETD Visit, if the subject agrees to return to the clinic.
- Occurrence of an AE or clinically significant laboratory abnormality that, in the opinion of the Investigator, warrants the subject's permanent discontinuation from study drug treatment; the Medical Monitor should be notified as soon as possible of any discontinuation of study drug due to an AE.

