6.4 Vital Status Follow-Up Phone Call

For randomized subjects who received at least 1 dose of study drug, conduct vital status telephone call approximately 3 months after last visit and approximately every 3 months thereafter or until subject enrolls in a separate open-label study, death, or for up to 5 years.

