7.4.3 Disease Progression and Death

Disease progression (including progression of hematologic condition and/or organ dysfunction of AL amyloidosis, and death due to disease progression) is generally recorded as part of the efficacy evaluation and should not be reported as a specific AE or SAE term. When an AE resulting from disease progression meets the requirements to be considered serious, the SAE verbatim term should be reported as the diagnosis that best describes the event rather than as “disease progression.” For instance, a subject with pleural effusion presents with shortness of breath. The cause of the shortness of breath is a pleural effusion resulting from disease progression. The event term may be reported as “pleural effusion” instead of disease progression.

Death should not be reported as an SAE term, but as a clinical outcome of a specific SAE. The cause of death, reported on a source document such as the Death Certificate or autopsy report, should be used as the event term for the SAE. For example, in a subject with acute heart failure that results in death, the SAE is reported as “acute heart failure” with an outcome of “death.”

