8.10.7.2. Cardiac Progression-Free Survival

Cardiac progression is defined as NT-proBNP progression of >30% increase and >300 ng/L increase or death. Cardiac progression will not be evaluated in the presence of renal progression, defined as an eGFR of < 30 mL/min/1.73 m², according to [Comenzo 2012 \(Appendix 2\)](#).

Progression-free survival is defined as the time from first infusion of study drug to the earliest of:

- first documented date of disease progression (as defined by NT-proBNP [Section 2.3.4.1.1]) or
- withdrawal from treatment or study due to organ (cardiac) progression or
- death on the study or
- death following withdrawal from treatment due to any cause.

Progression-free survival will be calculated in days as the earliest of the above dates (disease progression or death) minus the date of first infusion of study drug plus 1.

Subjects who are alive with no documented progression prior to the end of the study will be censored at the earliest of their date of the first assessment that meets renal progression (defined as an eGFR of < 30 mL/min/1.73 m²), date of the last NT-proBNP measurement, or date they withdraw consent or are lost to follow-up.

NEOD001 will be compared to placebo using the log rank test stratified by the randomization stratification factors. KM estimates of the distribution of the time-to-event will be tabulated and graphed by treatment group. The tabulation will include the KM estimate of the medians, 25th and 75th percentiles, and corresponding 95% CIs, if estimable. The tabular and graphical summaries will include the at-risk counts for every visit. The number and percent of subjects

censored and with events will be presented overall and for each visit, using last day of the visit window. The hazard ratio and 95% CI will be determined based on a Cox regression model stratified by randomization strata to estimate the magnitude of the effect.

In addition, a sensitivity analysis will be performed counting death or progression without subsequent response as an event.

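### SAP 8.10.7.4 counts any withdrawal recorded as disease progression as both cardiac and renal progression, without requiring that organ, and dates it at an undefined last contact

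*SAP*

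**What the plan says.** SAP 2.3.4.7 lists time to progression for heart and kidney separately, and for either organ. The organ events are laboratory-based: NT-proBNP for the heart (SAP 2.3.1) and an eGFR fall of at least 25% for the kidney (SAP 2.3.3.1).

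SAP 8.10.7.4 then adds two assumed events. The first is for deaths: a subject who dies with no progression yet on record counts as progressing on the day of death. The second is for those who stop "due to disease progression, as reported on the ETD or EOS eCRF, will be assumed to have progressed at the date of their last contact". Both sit in the sentence that introduces all three endpoints. Subjects without an event are censored at the last NT-proBNP (cardiac), the last eGFR (renal), or the earlier of the two (combined).

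For cardiac progression-free survival, SAP 8.10.7.2 includes in its event list "withdrawal from treatment or study due to organ (cardiac) progression or" (the list then goes on to death).

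Two protocol passages bear on the meaning of the term. Section 7.4.3 speaks of "Disease progression (including progression of hematologic condition and/or organ dysfunction of AL amyloidosis, and death due to disease progression"). Section 4.3 gives as the first reason for stopping drug "Hematologic progression and initiation of chemotherapy is required".

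Two more bear on contact after stopping. Willing subjects return for the ETD visit "and then have assessments monthly, through Month 12" (Section 4.3). Vital status calls are made about 3 months after the last visit and "approximately every 3 months thereafter or until subject enrolls in a separate open-label study, death, or for up to 5 years" (Section 6.4).

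**The concern.** An endpoint for one organ should record what happened to that organ. Here a single recorded reason, with no organ attached, creates an event in every endpoint that applies to the subject. Events that do not belong to the heart or kidney endpoint pull the comparison towards whatever the arms show on those other events. If the other events are balanced, the treatment difference is diluted.

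The date is a second problem. A subject with an assumed event runs to last contact, while a subject without one stops at the last measurement of the organ. Two subjects with the same follow-up can therefore have different time at risk only because of the withdrawal reason. A genuine early failure with no laboratory progression can also be shown as a longer progression-free time.

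**Working it through.** **Stated figures.** The documents give no event rate or power for these endpoints, so there is nothing to reproduce. The only sample-size figure, 91% power for the primary endpoint, reproduces at 91.3% (65 per arm, 50% vs 22.5%, pooled variance, two-sided 0.05) and does not depend on this rule.

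**Which organ.** Applying the sentence literally to a renal evaluable subject with no laboratory progression in the organ concerned:

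| Reason behind the recorded disease progression | Cardiac endpoint | Renal endpoint | Combined endpoint |
|---|---|---|---|
| Cardiac | event, correct | event, wrong organ | event, correct |
| Renal | event, wrong organ | event, correct | event, correct |
| Hematologic, if the eCRF reason covers it | event, no organ basis | event, no organ basis | event, no organ basis |

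The first two rows follow from the sentence itself. The third needs an eCRF reason that includes hematologic progression. Under the wording of SAP 8.10.7.2, only the cardiac row would count towards a cardiac event.

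**Which date.** SAP 8.10.7.4 computes months as study day / 30.4375. Take a last dose at the Month 4 target, Day 84 (SAP Table 3), so drug stops at 84 / 30.4375 = 2.8 months. The possible event dates are:

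- ETD visit is last contact: Day 84 + 30 = 114; 114 / 30.4375 = 3.7 months.
- First call about 91 days after ETD, if calls count: Day 205; 205 / 30.4375 = 6.7 months.
- Month 12 visit is last contact: Day 308; 308 / 30.4375 = 10.1 months.

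Now suppose a second subject stops on the same day for another reason, has the last NT-proBNP at ETD and takes the same call. That subject is censored at 3.7 months. If calls count, the first subject's event is at 6.7 months.

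The withdrawal clause also lacks the qualifier in the death clause that no progression has yet been documented. It does not say whether an earlier laboratory date takes precedence.

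**Size, crude.** These inputs are assumptions and are not in the documents: 65 per arm, 12 vs 20 true cardiac progressions, and 5% per arm (0.05 × 65 = 3.25, about 3) added by the rule, none of whom would otherwise have had an event.

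- Before: 12 / 20 = 0.60.
- After: (12 + 3) / (20 + 3) = 15 / 23 = 0.65.
- Share of events that are not cardiac: 6 / 38 = 16%.

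**Size, hazard ratio.** A Cox simulation used 400 replicates of 1,300 subjects, large enough to show bias rather than chance. It assumed a true organ hazard ratio of 0.50, 30% control-arm progression by Day 338, and equal non-organ withdrawal in both arms.

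| Non-organ withdrawals | Censored at withdrawal | Counted, dated at withdrawal | Counted, dated 3 to 12 months after Day 338 |
|---|---|---|---|
| 5% | 0.50 | 0.56 | 0.56 |
| 10% | 0.50 | 0.61 | 0.61 |
| 20% | 0.50 | 0.69 | 0.69 |

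In this set-up almost all of the shift comes from counting the events. The late date hardly moves the hazard ratio; its effect is on the Kaplan-Meier times.

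**The case against.** The strongest reply is that the trigger is an eCRF field that neither document shows. A reader might infer that hematologic progression will become organ progression. The documents do not establish this. Protocol 7.4.3 is a convention for reporting adverse events and does not define a withdrawal code. Protocol 4.3 lists hematologic progression as its own reason and has no general disease progression entry, so it does not show that the two share a code. This stands, and the hematologic route is conditional.

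It can also be said that the SAP means organ progression. Sections 8.10.7.2 and 8.10.7.3 tie disease progression to NT-proBNP, and the death clause of 8.10.7.4 uses the term for the organ event. That may be the intention, but it does not rescue the rule. One sentence still serves three endpoints, and reading the term as NT-proBNP progression would still turn cardiac withdrawals into renal events.

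On dates, a reader might infer from the 5-year calls that events could be placed years late, or at 18 months. The documents do not support this either. These endpoints are analyzed in the manner of SAP 8.10.7.1, where follow-up runs to the last subject's last visit, and Protocol 3.7 ends the study at the last EOS visit. The accrual period is not given. SAP 4.3 counts telephone contacts towards the last-known-alive date but does not say that they count as last contact.

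Three further limits are fair. NT-proBNP and chemistry are scheduled monthly, also after stopping for willing subjects, so many true progressions will have a laboratory date. For a purely hematologic withdrawal, a late date hides no organ failure. Cardiac progression-free survival already gives an organ-restricted cardiac analysis.

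**Conclusion.** The point holds for the rule as written. SAP 8.10.7.4 scores cross-organ events in the separate cardiac and renal endpoints, differs from SAP 8.10.7.2 on the parallel event, and uses an event date that it does not define and that differs from its own censoring date. Because it states a rule that gives wrong results when followed, this is more than missing detail. SAP Section 10 does not explain it.

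The combined endpoint is affected less. Cardiac and renal withdrawals belong there, so only its date and any withdrawals for neither organ are in question.

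The size cannot be fixed from the documents. The movement from 0.60 to 0.65, and the hazard ratios of 0.56 to 0.69 in place of 0.50, rest on assumed rates and on balanced added events; unbalanced events could move the estimate either way. The dating range of 3.7 to 10.1 months holds for a last dose on Day 84 without calls. Calls, if they count, could extend it up to the last subject's last visit.

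The endpoints are exploratory. The primary endpoint, key secondary endpoints and type I error are unaffected. It is worth correcting before unblinding because the correction is cheap.

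**What to change.** Revise SAP 8.10.7.4 as follows:

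- Count a discontinuation as cardiac progression only when the recorded reason is cardiac progression, and as renal progression only when it is renal progression. For the combined endpoint, accept either.
- Date the event at the first documented central-laboratory NT-proBNP or eGFR progression where there is one. Otherwise use the recorded date of treatment or study discontinuation, consistent with SAP 8.10.7.2. Do not use last contact.
- Leave all other discontinuations, including hematologic ones, on their own central laboratory data, and censor them at the last assessment of that organ if no progression is seen. Keep the existing death rule.

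The cost is SAP wording and one derivation. There will be slightly fewer events. The organ behind each recorded reason may have to be checked against the eCRF; the chemotherapy entries required by Protocol 4.3 help to identify hematologic withdrawals.

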8.10.7.5. Time to First Organ Response

The following time-to response endpoints will be analyzed in the same manner described in Section 8.10.7.1.

- Time (months) to first cardiac response calculated as: (date first assessed with response (Section 8.7) - the date of first study drug infusion + 1) / 30.4375. Subjects who do not respond will be censored at the date of last NT-proBNP assessment.
- For renal evaluable subjects, time (months) to first renal response calculated as: (date first assessed with response (Section 8.9.1) - the date of first study drug infusion + 1) / 30.4375. Subjects who do not respond will be censored at the date of last proteinuria (urine total protein) assessment.
- Time (months) to cardiac or renal response calculated as: (earliest date assessed as a cardiac or renal responder - the date of first study drug infusion + 1) / 30.4375. Subjects who do not respond will be censored at the minimum of the last NT-proBNP assessment date, last proteinuria (urine total protein) assessment date, or last eGFR assessment date.

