3. SAMPLE SIZE JUSTIFICATION

For the primary endpoint, the assumed true rates for NEOD001 vs placebo are 50% and 22.5%, respectively. Based on a two-sample comparison of proportions at the $\alpha=0.05$ level of significance, a total sample size of 100 subjects (50 in the NEOD001 arm, 50 in the placebo arm) will provide $>80\%$ power based on a two-sided Cochran-Mantel-Haenszel (CMH) test. Based on the actual enrolled sample size ($N\sim 130$), the final power is 91%.

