8.2.1. Time to Event Endpoints

Censoring rules are defined in the applicable study endpoint section (Section 8.10.7). Subjects with no data after randomization will be censored on Day 1 (first day of study drug dosing). As a sensitivity analysis, subjects with no data after randomization will be considered to have an event on Day 1 (first day of study drug dosing). These sensitivity analyses will only be performed for analyses where death or progression are events and only in cases where at least one subject is missing the relevant post-randomization data. Methods for handling missing data for time to event endpoints are included in the applicable study endpoint section because the censoring and event dates are specific to the events being analyzed.

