8.2.2. Responder Endpoints

The primary analysis for best response analyses will consider a subject as a non-responder until a response is achieved.

For other categorical efficacy endpoints in which subjects are classified as either a responder or a non-responder (binary outcome) based on dichotomizing a continuous variable at each visit, analyses will use “observed cases,” where subjects who do not provide an assessment at the specified time point for the defining of response will not be included. That is, for the percentage of responders, the subject will not be included in the numerator or the denominator. To assess the effect of missing data as a sensitivity analyses, any subject who does not provide an assessment at the specified time point for the response definition will be considered as a non-responder, regardless of treatment group. For analyses using a 3-category response (response, stable, progression), any subject who does not provide an assessment at the specified time point for the defining of response will be considered to have progressed, regardless of treatment group.

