8.10.7. Additional Time-to-Event Endpoints

8.10.7.1. Time to All-Cause Mortality (Overall Survival)

Overall survival, time to all-cause mortality, will be calculated in days as the date of death minus the date of first study drug infusion plus 1. Subjects will be censored at their last assessment known to be alive prior to LSLV.

NEOD001 will be compared to placebo using the log rank test stratified by the randomization stratification factors. Kaplan-Meier (KM) estimates of the distribution of the time-to-event will be tabulated and graphed by treatment group. The tabulation will include the KM estimate of the medians, 25th and 75th quartiles, and corresponding 95% CIs, if estimable. The tabular and graphical summaries will include the at-risk counts for every visit. The number and percent of subjects censored and with events will be presented. The hazard ratio and 95% CI will be determined based on a Cox regression model stratified by randomization strata to estimate the magnitude of the effect.

In addition, the frequency of deaths in NEOD001 and placebo will be analyzed in the same manner described in Section 8.7 for the primary efficacy endpoint.

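### Time to first organ response censors subjects who die without responding, so the Kaplan-Meier curves overstate the cumulative share responding and their time percentiles fall too early

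*SAP*

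**What the plan says.** SAP 8.10.7.5 defines three endpoints: time to first cardiac response, time to first renal response, and time to either. For cardiac response, "Subjects who do not respond will be censored at the date of last NT-proBNP assessment". For renal response, "Subjects who do not respond will be censored at the date of last proteinuria (urine total protein) assessment". The composite is censored at the earliest of the last NT-proBNP, proteinuria and eGFR dates. None of the three has a rule for death.

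The method is borrowed from overall survival: "The following time-to response endpoints will be analyzed in the same manner described in Section 8.10.7.1". In that section, "Kaplan-Meier (KM) estimates of the distribution of the time-to-event will be tabulated and graphed by treatment group", with median and quartiles, a stratified log-rank test, a stratified Cox model, and the number and percentage of subjects censored and with events.

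Three other places bear on death:
- SAP 8.10.7.4, for progression only: "subjects who die prior to having documented disease progression will be assumed to have progressed at their date of death".
- SAP 8.2.1 leaves censoring to the endpoint sections and adds a sensitivity analysis for subjects without post-randomization data, with this limit: "These sensitivity analyses will only be performed for analyses where death or progression are events". Response is not covered.
- SAP 8.2.2, for binary best response: "The primary analysis for best response analyses will consider a subject as a non-responder until a response is achieved".

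SAP Section 10, which lists changes from the protocol, does not touch the point. Neither document plans a cumulative-incidence or competing-risk analysis.

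**The concern.** Kaplan-Meier gives the weight of a censored subject to those still at risk. That suits a subject whose later course is merely unobserved. A subject who has died cannot respond, so one minus Kaplan-Meier no longer estimates the proportion who respond by a given time.

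Nor can the curve safely be read as the response rate that would be seen without deaths, because that reading needs death and response to be independent. Protocol 1.2 and SAP 2.3.2.3 both say that falling NT-proBNP predicts lower mortality.

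At stake is how the response curves and their tabulated percentiles are described. Under best response a death without response is a non-response. In the time-to-response curve for the same NT-proBNP criterion, the same subject is treated as still able to respond.

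**Working it through.** **Inputs**
- Response rates, SAP Section 3: "the assumed true rates for NEOD001 vs placebo are 50% and 22.5%, respectively".
- Sample size: up to 130, randomized 1:1, so 65 per arm.
- Share dying without response: not given for this trial. I assume 5% to 15%. The only mortality figure in the documents is 14.7% (Protocol 1.3.2), from a different study in newly diagnosed subjects.

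**The plan's own figure.** The documents give no figure for time to response. The stated power can be checked: [0.275√n − 1.96√(2 × 0.3625 × 0.6375)] / √(0.25 + 0.225 × 0.775) gives 91.3% at n = 65 per arm (stated 91%) and 82.6% at n = 50 (stated above 80%). Both reproduce, and this point does not affect them.

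**Size of the overstatement.** Let R be the share who respond and D the share who die without responding by 12 months. If the ratio of the response hazard to the death hazard is constant (true for constant hazards and for event times uniform over the year), cumulative incidence equals R, while

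1 − KM = 1 − (1 − R − D)^(R/(R+D)).

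Example, R = 0.50 and D = 0.10: −ln(0.40) = 0.916; × 0.50/0.60 = 0.764; 1 − exp(−0.764) = 0.534.

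| D | R = 22.5% reads | R = 50% reads |
|---|---|---|
| 0% | 22.5% | 50.0% |
| 5% | 23.1% (+0.6) | 51.6% (+1.6) |
| 10% | 23.8% (+1.3) | 53.4% (+3.4) |
| 15% | 24.6% (+2.1) | 55.4% (+5.4) |

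**Worked count.** Of 65 subjects, 16 respond, then 7 die without response, then 17 more respond. The share responding is 33/65 = 50.8%. One minus Kaplan-Meier is 1 − (49/65) × (25/42) = 55.1%.

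**Simulation.** Visits every 28 days to Day 308 plus Day 338, censoring at the last assessment, independent constant hazards, one million subjects per scenario. With a no-death response rate of 50% and 12-month mortality of 5%, 10%, 14.7% and 20%, one minus Kaplan-Meier stays at about 50%, while 48.8%, 47.5%, 46.4% and 45.1% actually respond.

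**Percentiles.** With uniform times, 1 − KM at month t is 1 − (1 − (R+D)t/12)^(R/(R+D)).
- R = 0.50, D = 0.10: the curve reaches 50% when (1 − 0.60t/12)^0.833 = 0.5, that is at 11.3 months. Cumulative incidence reaches 50% at month 12.
- R = 0.48, D = 0.10: 1 − 0.42^0.828 = 51.2%. A median would be reported although fewer than half respond.
- R = 0.225: for D of 5% to 15% the curve stays below 25%, so no quartile is estimable in that arm.

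**The case against.** The strongest reply is that the plan already reports death-inclusive response proportions. Cardiac best response is analysed through 3, 6, 9 and 12 months (SAP 8.7, 8.10.1.1), as is renal best response (8.9.1, 8.10.4.1), and deaths stay in the denominator. The event counts required by 8.10.7.1 put the crude share responding beside the curve. The endpoint is exploratory and outside the hierarchy in SAP 8.6. At 5% deaths the excess is 0.6 to 1.6 points, and one subject in 65 is already 1.5 points. All of this stands and limits the weight of the point. It does not make the curve or its percentiles correct.

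Some stronger readings are tempting, and the documents do not support them:
- *The treatment comparison is invalid.* It is not. The stratified log-rank and Cox analyses compare cause-specific response hazards, for which censoring at death is standard. Gray's test addresses a different quantity, the cumulative incidence, so replacing the log-rank test with it is a choice of estimand and not a correction.
- *The arm with more deaths will look better.* With equal response hazards and independent deaths, the simulation gives equal curves whatever the mortality. The contrast arises if the share responding is held equal: 50% in both arms, with 5% versus 15% dying, reads 51.6% versus 55.4%. The arm with more deaths then has the higher response hazard among survivors.
- *The reported response rates are inflated.* The plan takes response percentages from best response and nowhere presents one minus Kaplan-Meier as a response rate.

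**Conclusion.** The point holds as a limited one. Under SAP 8.10.7.5 deaths without response are censored, and no other section corrects this. As an estimate of the cumulative share responding, one minus Kaplan-Meier is too high whenever such a death precedes a later response, and never too low for this reason. The time percentiles, where estimable, are too early.

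The size rests on an assumed death rate and a constant ratio of hazards. For 5% to 15% dying without response, the excess is 0.6 to 2.1 points at a true 22.5% and 1.6 to 5.4 points at a true 50%. It is zero with no deaths. The primary endpoint, the secondary best-response endpoints and the 3-, 6- and 9-month landmarks are unaffected.

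A reader might also infer that correcting this would make the 12-month point of the curve equal the primary response rate. It would not do so exactly: subjects who drop out alive remain censored in the curve, whereas SAP 8.2.2 counts them as non-responders.

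**What to change.** In SAP 8.10.7.5, replace the Kaplan-Meier curves and percentiles with Aalen-Johansen cumulative incidence of first response by arm, for all three endpoints, with death without response as a competing event. Keep the stratified log-rank and Cox results, labelled as cause-specific. A stratified Gray's test may be added as a supplement.

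Keeping subjects who die in the risk set to the end of follow-up is not an equivalent shortcut once living subjects drop out. Take 100 subjects: 10 die, 45 of the 90 living drop out, and 9 of the remaining 45 respond. Cumulative incidence is 0.9 × 9/45 = 18.0%. Keeping the dead at risk gives 9/55 = 16.4%. The best-response rule gives 9/100 = 9%, which also shows why the text should not promise an exact match with the primary rate.

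The cost is a change of SAP wording and a little extra programming, with no new data. The curves will look slightly less favourable.
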